5.2.1.4 Dose Modification

Adverse events (both non-serious and serious) associated with pembrolizumab exposure may represent an immunologic etiology. These adverse events may occur shortly after the first dose or several months after the last dose of treatment. Pembrolizumab must be withheld for drug-related toxicities and severe or life-threatening AEs as per Table 4 below. See [Section 5.4.1](#) and Events of Clinical Interest Guidance Document for supportive care guidelines, including use of corticosteroids.

Dose escalations or de-escalations of pembrolizumab are not allowed.

SQ IL-2 must be withheld for drug-related toxicities and severe or life-threatening AEs as per Table 4 below. SQ IL-2 associated with AE's requiring treatment interruption can be restarted at a reduced dose not lower than a 50% reduction of the recommended 125,000 U/kg dose.

If possible, the Investigator may attribute each toxicity event to pembrolizumab or IL-2 alone with a resulting dose modification applied to a single study drug. For example, local IL-2 injection site reaction could result in a hold of SQ IL-2 dosing with pembrolizumab continued without interruption.

Patients enrolled into Dose Level 3 who require treatment interruption and meet restarting criteria as described in Table 4 may have IL-2 dosing de-escalated to Dose Level 2 for the subsequent treatment cycle or course(s). Individual patient IL-2 dosing cannot be escalated.

Table 4 Dose Modification Guidelines for Drug-Related Adverse Events

General instructions:				
Immune-related AEs	Toxicity grade or conditions (CTCAEv5.0)	Action taken to pembrolizumab	irAE management with corticosteroid and/or other therapies	Monitor and follow-up
Pneumonitis	Grade 2	Withhold	
 Administer corticosteroids (initial dose of 1-2 mg/kg prednisone or equivalent) followed by taper 	
 Monitor participants for signs and symptoms of pneumonitis Evaluate participants with suspected pneumonitis with radiographic imaging and initiate corticosteroid treatment
	Grade 3 or 4, or recurrent Grade 2	Permanently discontinue		
Diarrhea / Colitis	Grade 2 or 3	Withhold	
 Administer corticosteroids (initial dose of 1-2 mg/kg prednisone or equivalent) followed by taper 	
 Monitor participants for signs and symptoms of enterocolitis (ie, diarrhea, abdominal pain, blood or mucus in stool with or without fever) and of bowel perforation (ie, peritoneal signs and ileus). Participants with \ge Grade 2 diarrhea suspecting colitis should consider GI consultation and performing endoscopy to rule out colitis. Participants with diarrhea/colitis should be advised to drink liberal quantities of clear fluids. If sufficient oral fluid intake is not feasible, fluid and electrolytes should be substituted via IV infusion.
	Recurrent Grade 3 or Grade 4	Permanently discontinue		

AST / ALT elevation or Increased bilirubin	Grade 2	Withhold	
 Administer corticosteroids (initial dose of 0.5- 1 mg/kg prednisone or equivalent) followed by taper 	
 Monitor with liver function tests (consider weekly or more frequently until liver enzyme value returned to baseline or is stable)
	Grade 3 or 4	Permanently discontinue	
 Administer corticosteroids (initial dose of 1-2 mg/kg prednisone or equivalent) followed by taper 	
Type 1 diabetes mellitus (T1DM) or Hyperglycemia	Newly onset T1DM or Grade 3 or 4 hyperglycemia associated with evidence of β -cell failure	Withhold	
 Initiate insulin replacement therapy for participants with T1DM Administer anti-hyperglycemic in participants with hyperglycemia 	
 Monitor participants for hyperglycemia or other signs and symptoms of diabetes.
Hypophysitis	Grade 2	Withhold	
 Administer corticosteroids and initiate hormonal replacements as clinically indicated. 	
 Monitor for signs and symptoms of hypophysitis (including hypopituitarism and adrenal insufficiency)
	Grade 3 or 4	Withhold or permanently discontinue ¹		
Hyperthyroidism	Grade 2	Continue	
 Treat with non-selective beta-blockers (eg, propranolol) or thionamides as appropriate 	
 Monitor for signs and symptoms of thyroid disorders.
	Grade 3 or 4	Withhold or permanently discontinue ¹		
Hypothyroidism	Grade 2-4	Continue	
 Initiate thyroid replacement hormones (eg, levothyroxine or liothyronine) per standard of care 	
 Monitor for signs and symptoms of thyroid disorders.
Nephritis and Renal dysfunction	Grade 2	Withhold	
 Administer corticosteroids (prednisone 1-2 mg/kg or equivalent) followed by taper. 	
 Monitor changes of renal function
	Grade 3 or 4	Permanently discontinue		
Neurological Toxicities	Grade 2	Withhold	
 Based on severity of AE administer corticosteroids 	
 Ensure adequate evaluation to confirm etiology and/or exclude other causes
	Grade 3 or 4	Permanently discontinue		
Myocarditis	Asymptomatic Troponin Elevation	Withhold	
 Consider corticosteroids 	
 Repeat and monitor troponin Consider Cardiology consultation for further diagnostic workup
	Grade 2	Permanently discontinue	
 Administer corticosteroids (prednisone 2 mg/kg or equivalent) 	
 Hospitalization Urgent cardiology consultation for evaluation and management Taper steroid over at least 1 month with close monitoring Repeat cardiac MRI post treatment
	Grade 3 or 4	Permanently discontinue	
 Immediate initiation of corticosteroids (prednisone 2 mg/kg or equivalent or 1 g IV bolus) Consider adding second immunosuppressive agent 	
 Hospitalization to intensive cardiac care unit Emergent cardiology consultation for evaluation and management Taper steroid over at least 1 month with close monitoring Repeat cardiac MRI post treatment

Exfoliative Dermatologic Conditions	Suspected SJS, TEN, or DRESS	Withhold	
 Based on severity of AE administer corticosteroids 	
 Ensure adequate evaluation to confirm etiology or exclude other causes
	Confirmed SJS, TEN, or DRESS	Permanently discontinue		
All other immune-related AEs	Intolerable/persistent Grade 2	Withhold	
 Based on type and severity of AE administer corticosteroids 	
 Ensure adequate evaluation to confirm etiology and/or exclude other causes
	Grade 3	Withhold or discontinue based on the type of event.		
	Grade 4 or recurrent Grade 3	Permanently discontinue		

AE(s)=adverse event(s); ALT=alanine aminotransferase; AST=aspartate aminotransferase; CTCAE=Common Terminology Criteria for Adverse Events; DRESS=Drug Rash with Eosinophilia and Systemic Symptom; GI=gastrointestinal; IO=immuno-oncology; ir=immune related; IV=intravenous; SJS=Stevens-Johnson Syndrome; T1DM=type 1 diabetes mellitus; TEN=Toxic Epidermal Necrolysis; ULN=upper limit of normal.

¹NOTES:

- For participants with Grade 3 or 4 immune-related endocrinopathy where withhold of pembrolizumab is required, pembrolizumab may be resumed when AE resolves to \leq Grade 2 and is controlled with hormonal replacement therapy or achieved metabolic control (in case of T1DM).
- The decision to withhold or permanently discontinue pembrolizumab is at the discretion of the investigator or treating physician. If control achieved or \leq Grade 2, pembrolizumab may be resumed.

Dosing interruptions are permitted in the case of medical / surgical events or logistical reasons not related to study therapy (e.g., elective surgery, unrelated medical events, patient vacation, and/or holidays). Subjects should be placed back on study therapy within 3 weeks of the scheduled interruption, unless otherwise discussed with the Principal Investigator. The reason for interruption should be documented in the patient's study record.

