5.2.1.3 Definition of Dose-Limiting Toxicities

All toxicities will be graded using the National Cancer Institute (NCI) CTCAE v5.0 (Appendix 2; Section 13.2). Dose-limiting toxicity (DLT) assessment will be based on events occurring during the DLT assessment period, which is defined as course 1. Dose-limiting toxicities include all adverse experiences that are clearly not related to disease progression or intercurrent illness if judged by the investigator to be possibly, probably, or definitely related to study treatments that meet or exceed the following severity criteria:

- Toxicities associated with pembrolizumab representing autoimmune phenomenon have been extensively characterized, and may be exacerbated by combination treatment with IL-2. Treatment associated AE's that represent immune mediated pathology are codified in [Section 5.2.1.4](#), Table 4. For patients at Dose Level 1, all AE's resulting in Guideline recommendation for Treatment Discontinuation will also constitute a DLT.
- A delay in the scheduled administration of either component of therapy of > 21 days for pembrolizumab or SQ or IV bolus IL-2.
- Bolus IV dosing of IL-2 (Dose Level 2 and 3), especially at Dose Level 3, is known to be associated with acute severe toxicities. Doses are administered to patient tolerance according to established treatment guidelines (Appendix 4, Section 13.4). Toxicities associated with IL-2 administration will be initially managed according to the IL-2 Toxicity Management Guidelines (Appendix 4, Section 13.4). Toxicities that fail to stabilize within 48 hours of the last IL-2 dose or that fail to show improvement within 72 hours of the last IL-2 dose will convert to management according to [Section 5.2.1.4](#), Table 4 and resulting AE grade and Treatment Discontinuation assignment forming the basis for DLT determination.
- Grade 5 toxicity

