8.1.1 Accrual and Study Progress Oversight

The Principal Investigator will direct the formation of a Safety Data Review Board (SDRB) that will review study accrual and provide direction for dose escalations based on analysis of collected safety data including AE's, SAE's and DLT's. The SDRB will consist of the Principal Investigator, designated sub-investigators, and study administrative staff. Meetings will occur after completion of each dose-level cohort and on an as needed basis to address unanticipated adverse events. Meeting minutes will be documented. Any significant safety findings will be reported to Fred Hutch/University of Washington Cancer Consortium Institutional Review Board (IRB).

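### Three severe-event entries in Table 4 allow two actions, so DLT status for the same event and grade can turn on an open-label treatment choice unless a delay of more than 21 days settles it

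*Combined protocol and SAP*

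**What the plan says.** **DLT definition (Section 5.2.1.3).** There is no general Grade 3-4 criterion; immune toxicity reaches DLT status through Table 4.
- Dose Level 1: "For patients at Dose Level 1, all AE's resulting in Guideline recommendation for Treatment Discontinuation will also constitute a DLT".
- Dose Levels 2 and 3: IL-2 toxicity passes to Table 4 only if it has not stabilised 48 hours, or not improved 72 hours, after the last IL-2 dose. The text then has "resulting AE grade and Treatment Discontinuation assignment forming the basis for DLT determination", with no grade threshold.
- Two other routes: Grade 5 toxicity, and "A delay in the scheduled administration of either component of therapy of > 21 days for pembrolizumab or SQ or IV bolus IL-2".

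**Table 4 (Section 5.2.1.4).** Three entries give two actions.
- Hypophysitis and hyperthyroidism, each at Grade 3 or 4: "Withhold or permanently discontinue", marked with footnote 1. The notes under that footnote state: "The decision to withhold or permanently discontinue pembrolizumab is at the discretion of the investigator or treating physician". They let pembrolizumab resume once the event is controlled or at Grade 2 or lower.
- All other immune-related events at Grade 3: "Withhold or discontinue based on the type of event". This entry carries no footnote marker, and the types are not listed.

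The other entries name one action each. Permanent discontinuation is fixed for Grade 3-4 pneumonitis, hepatic, renal, neurological and myocarditis events, and for Grade 4 or recurrent Grade 3 events in the catch-all.

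**Escalation and oversight.** Under Section 5.2.1.2, no DLT in 3 opens the next level, 1 in 3 expands the cohort to 6, 1 in 6 opens the next level, and 2 or more exceed the MTD. The trial is open-label (Section 5.2.3). Section 8.1.1 has a safety board direct escalation: "The SDRB will consist of the Principal Investigator, designated sub-investigators, and study administrative staff".

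**The concern.** A 3+3 count is only as reproducible as the DLT definition behind it. Here the definition points to a table entry, and in three entries the table names two actions, one of which makes the event a DLT and one of which does not. For the endocrine entries the choice passes to the physician, without criteria. A treatment judgement made with full knowledge of the dose level can then settle the DLT count, although neither the event nor its grade differs between patients.

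Escalation is the main decision in a study of 12 to 15 patients whose primary objective is safety. One patient counted differently is enough to change it.

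**Working it through.** The plan states no DLT rate, target toxicity or operating characteristic, so there is no figure of its own to reproduce. The check has three parts.

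**1. Does the text resolve the open entries?** At Dose Level 1 the test is a guideline recommendation to discontinue. In the three entries the guideline offers both withholding and discontinuing. For two of them it then refers to the physician, and for the third to unlisted event types. At Dose Levels 2 and 3 the basis is grade plus discontinuation assignment, but with no threshold grade does not settle the matter either. The text therefore leaves status open.

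**2. How far does the 21-day rule close the gap?** Using nominal days from the flow chart (Section 6.1), pembrolizumab in course 1 falls in weeks 1, 4, 7 and 10, that is days 1, 22, 43 and 64. Course 1 ends on day 12 × 7 = 84.
- An event that delays a dose by more than 21 days is a DLT whichever action was chosen.
- An event after which dosing resumes within 21 days of schedule is not caught. The Table 4 notes permit resumption on control or at Grade 2 or lower.
- If the day 64 dose is the one held, 64 + 21 = 85, so a delay of more than 21 days cannot be reached within course 1.
- An event after the day 64 dose has no further course 1 dose to delay, because SQ IL-2 ends in week 6 and IV IL-2 on day 27.
- DLTs after course 1 do not enter the escalation count. Section 5.2.1.2 only holds accrual if two or more occur in a cohort.

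**3. What can one reclassification do?** Suppose 2 of 3 patients have Grade 3 hypophysitis at Dose Level 1, with no other DLT.
- Both discontinued: 2/3, the level exceeds the MTD.
- One discontinued, one withheld and resumed within 21 days: 1/3, expand to 6.
- Both withheld and resumed within 21 days: 0/3, the next level opens.

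For probabilities, let p be the per-patient DLT probability:

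P(clear) = (1 − p)³ + 3p(1 − p)² × (1 − p)³

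The rates are assumptions: 15% have another DLT, a further 10% have only an open-entry event, and no held event becomes a DLT by delay.
- None counted, p = 0.15: 0.6141 + 0.3251 × 0.6141 = 0.814.
- All counted, p = 0.25: 0.4219 + 0.4219 × 0.4219 = 0.600.

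If the open-entry rate is 5% or 15% instead, the all-counted value is 0.709 (p = 0.20) or 0.494 (p = 0.30). If half of the 10% become DLTs by delay in any case, the none-counted value falls to 0.709 (p = 0.20), and the contrast narrows to 71% against 60%.

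The next table treats the two kinds of event as independent, with p = 1 − (1 − q)(1 − d), where q is the rate of other DLTs and d the rate of open-entry events. All rates are assumed.

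| q | d | none counted | all counted |
|---|---|---|---|
| 5% | 5% | 97.3% | 91.0% |
| 10% | 10% | 90.6% | 73.0% |
| 15% | 10% | 81.4% | 63.2% |
| 20% | 20% | 70.9% | 37.8% |

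**The case against.** **The test is the guideline, not the physician's act.** That is the wording at Dose Level 1, and it is a fair reading. It does not help in these entries, because the guideline itself gives two answers. The root defect is an undefined table entry; dependence on the treatment choice follows from it.

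**The 21-day rule is a backstop.** This stands in part. A reader might infer that Grade 4 hypophysitis is never a DLT once pembrolizumab is withheld and resumed. The documents do not support that, since a delay of more than 21 days is a DLT by itself. Section 5.4.1 also calls for corticosteroids in both endocrine conditions, tapered over at least 4 weeks once symptoms improve to Grade 1 or less, which may lengthen some holds. No text bars resuming during the taper, so the rule narrows the gap without closing it.

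**Most severe events are unaffected.** This stands. The note on physician discretion attaches only to the two endocrine entries. The catch-all is open at Grade 3 only and states a criterion, though an undefined one. A separate guidance document on events of clinical interest is cited and was not available here. At Dose Levels 2 and 3 the issue reaches only IL-2 toxicity that fails the 48/72-hour tests.

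**Conflict of interest.** A reader might infer that the physicians who choose the treatment also direct escalation, and that the count is biased towards escalating. The documents show neither. The discretion belongs to the investigator or treating physician, while the board seats the Principal Investigator, designated sub-investigators and staff. Overlap is possible but not stated, and the direction of any bias is conjecture. Open-label conduct is not itself a fault in a 3+3 study, and Section 8.1.2 provides institutional committee review at least annually and as needed.

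**Conclusion.** The point holds as a narrow gap in the DLT definition. In three Table 4 entries, DLT status for the same event and grade can depend on an open-label treatment choice when dosing resumes within 21 days, or when the event occurs late in course 1 with no further dose due. One such patient moves a cohort from 0/3 to 1/3 or from 1/3 to 2/3.

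Confidence is high that the text leaves these entries open. The size of the effect is not known. The contrast of 81% with 60% is an outer bound, since it compares counting none with counting all, on rates that the documents do not supply, with no DLTs by delay. It should not be read as an expected bias.

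**What to change.** Reconcile Section 5.2.1.3 with Table 4. Give each of the three open entries one DLT status by event and CTCAE grade, chosen by the sponsor and set before the next cohort is assessed. For the catch-all, this means either one status for all Grade 3 events or a list of types with a default for anything unlisted. State that the status applies whether pembrolizumab was in fact withheld or stopped, and that it also serves toxicity passing to Table 4 at Dose Levels 2 and 3. Keep the rule on delays of more than 21 days, and leave the physician's treatment discretion unchanged. Which status each entry should have is not judged here.

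The cost is one added column or a short list. The team must settle in advance how each entry counts, including hormone-controlled endocrine events, and some events may count differently than they would under case-by-case judgement.

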5.2.2 Timing of Dose Administration

Trial treatment should begin on Day 1 of each cycle after all procedures/assessments have been completed as detailed on the Trial Flow Chart (Section 6.0).

All pembrolizumab treatments will be administered on an outpatient basis.

Pembrolizumab 200 mg will be administered as a 30 minute IV infusion every 3 weeks (± 2 days, see Section 6.0). Every effort should be made to target infusion timing to be as close to 30 minutes as possible. However, given the variability of infusion pumps, a window of -5 minutes and +10 minutes is permitted (i.e., infusion time is 30 minutes: -5 min/+10 min).

IL-2 administration will follow pembrolizumab dosing for all cohorts. Outpatient SQ IL-2 dosing will begin on cycle day 1 after completion of the pembrolizumab infusion. For day 1 cycle 1, patients should be observed \geq 1 hour after completion of pembrolizumab before the first SQ IL-2 dose.

Patients will be admitted on cycle day 2 (or the next available ICU admission day) to begin IV IL-2 treatments for Cohorts 2 and 3.

5.2.3 Trial Blinding/Masking

This is an open-label trial; therefore, the Sponsor, investigator and subject will know the treatment administered.

5.3 Concomitant Medications/Vaccinations (allowed & prohibited)

Medications or vaccinations specifically prohibited in the exclusion criteria are not allowed during the ongoing trial. If there is a clinical indication for one of these medications or vaccinations specifically prohibited during the trial, discontinuation from trial therapy may be required. The investigator should discuss any questions regarding this with the Merck Clinical team. The final decision on any supportive therapy or vaccination rests with the investigator or the Principal Investigator.

5.3.1 Acceptable Concomitant Medications

All treatments that the investigator considers necessary for a subject's welfare may be administered at the discretion of the investigator in keeping with the community standards of medical care. All concomitant medication will be recorded on the case report form (CRF) including all prescription, over-the-counter (OTC), herbal supplements, and IV medications and fluids. If changes occur during the trial period, documentation of drug dosage, frequency, route, and date may also be included on the CRF.

All concomitant medications for the treatment of preexisting conditions in use immediately prior to the start of study treatment and/or up to 30 days after the last dose of trial treatment should also be recorded. Concomitant medications administered after 30 days after the last dose of trial treatment should be recorded for SAEs and ECIs as defined in Section 7.3.

5.3.2 Prohibited Concomitant Medications

Subjects are prohibited from receiving the following therapies during the Screening, Treatment, and Follow-Up phases of this trial:

- Anti-cancer systemic chemotherapy or biological therapy
- Immunotherapy not specified in this protocol
- Chemotherapy not specified in this protocol
- Investigational agents other than pembrolizumab
- Radiation therapy
 - Note: Radiation therapy to a symptomatic solitary lesion or to the brain may be allowed after consultation with Principal Investigator.
- Live vaccines within 30 days prior to the first dose of trial treatment and while participating in the trial. Examples of live vaccines include, but are not limited to, the following: measles, mumps, rubella, chicken pox, yellow fever, rabies, BCG, and typhoid (oral) vaccine. Seasonal influenza vaccines for injection are generally killed virus

vaccines and are allowed; however intranasal influenza vaccines (e.g. Flu-Mist®) are live attenuated vaccines, and are not allowed.

- Glucocorticoids for any purpose other than to modulate symptoms from an event of clinical interest of suspected immunologic etiology. The use of physiologic doses of corticosteroids may be approved after consultation with the Principal Investigator.

Subjects who, in the assessment by the investigator or Principal Investigator, require the use of any of the aforementioned treatments for clinical management should be removed from the trial. Subjects may receive other medications that the investigator deems to be medically necessary.

The Exclusion Criteria describes other medications which are prohibited in this trial.

There are no prohibited therapies during the Post-Treatment Follow-Up Phase.

5.4 Rescue Medications & Supportive Care

5.4.1 Supportive Care Guidelines

Subjects should receive appropriate supportive care measures as deemed necessary by the treating investigator. Suggested supportive care measures for the management of adverse events with potential immunologic etiology are outlined below. Where appropriate, these guidelines include the use of oral or intravenous treatment with corticosteroids as well as additional anti-inflammatory agents if symptoms do not improve with administration of corticosteroids. Note that several courses of steroid tapering may be necessary as symptoms may worsen when the steroid dose is decreased. For each disorder, attempts should be made to rule out other causes such as metastatic disease or bacterial or viral infection, which might require additional supportive care. The treatment guidelines are intended to be applied when the investigator determines the events to be related to pembrolizumab.

Note: if after the evaluation the event is determined not to be related, the investigator does not need to follow the treatment guidance (as outlined below). Refer to [Section 5.2.1](#) for dose modification.

It may be necessary to perform conditional procedures such as bronchoscopy, endoscopy, or skin photography as part of evaluation of the event.

- **Pneumonitis:**
 - For **Grade 2 events**, treat with systemic corticosteroids. When symptoms improve to Grade 1 or less, steroid taper should be started and continued over no less than 4 weeks.
 - For **Grade 3-4 events**, immediately treat with intravenous steroids. Administer additional anti-inflammatory measures, as needed.
 - Add prophylactic antibiotics for opportunistic infections in the case of prolonged steroid administration.
- **Myocarditis**

- For **Asymptomatic Troponin Elevation**, repeat and monitor troponin. Perform further diagnostic workup; ECG, cardiac MRI and consider Cardiology consultation. Consider corticosteroids if troponin doesn't normalize.
- For **Grade 2 events**, hospitalize patients to expedite Cardiology consultation and evaluation.
 - Troponin and BNP; ECG and continuous cardiac monitoring; Echocardiogram and Cardiac MRI.
 - Administer prednisone or equivalent at 2 mg/kg.
 - Upon recovery, taper steroids over at least 1 month with close monitoring by lab testing and new symptoms. Repeat cardiac MRI post treatment.
- For **Grade 3-4 events**, hospitalize to intensive cardiac care unit with heart failure therapy as needed. Emergent Cardiology evaluation
 - Troponin and BNP; ECG and continuous cardiac monitoring; Echocardiogram and Cardiac MRI.
 - Myocardial biopsy if feasible
 - Immediate initiation of immunosuppression with prednisone or equivalent at 2 mg/kg or 1 g IV bolus. Consider adding a second immunosuppressive agent, such as ATG
 - Upon recovery, taper steroids over at least 1 month with close monitoring by lab testing and new symptoms. Repeat cardiac MRI post treatment.
- **Diarrhea/Colitis:**

Subjects should be carefully monitored for signs and symptoms of enterocolitis (such as diarrhea, abdominal pain, blood or mucus in stool, with or without fever) and of bowel perforation (such as peritoneal signs and ileus).

 - All subjects who experience diarrhea/colitis should be advised to drink liberal quantities of clear fluids. If sufficient oral fluid intake is not feasible, fluid and electrolytes should be substituted via IV infusion. For Grade 2 or higher diarrhea, consider GI consultation and endoscopy to confirm or rule out colitis.
 - For **Grade 2 diarrhea/colitis**, administer oral corticosteroids.
 - For **Grade 3 or 4 diarrhea/colitis**, treat with intravenous steroids followed by high dose oral steroids.
 - When symptoms improve to Grade 1 or less, steroid taper should be started and continued over no less than 4 weeks.
- **Type 1 diabetes mellitus (if new onset, including diabetic ketoacidosis [DKA]) or ≥ Grade 3 Hyperglycemia, if associated with ketosis (ketonuria) or metabolic acidosis (DKA)**
 - For **T1DM** or **Grade 3-4 Hyperglycemia**

- Insulin replacement therapy is recommended for Type I diabetes mellitus and for Grade 3-4 hyperglycemia associated with metabolic acidosis or ketonuria.
- Evaluate patients with serum glucose and a metabolic panel, urine ketones, glycosylated hemoglobin, and C-peptide.
- **Hypophysitis:**
 - For **Grade 2-4** events, treat with corticosteroids. When symptoms improve to Grade 1 or less, steroid taper should be started and continued over no less than 4 weeks. Replacement of appropriate hormones may be required as the steroid dose is tapered.
- **Hyperthyroidism or Hypothyroidism:**

Thyroid disorders can occur at any time during treatment. Monitor patients for changes in thyroid function (at the start of treatment, periodically during treatment, and as indicated based on clinical evaluation) and for clinical signs and symptoms of thyroid disorders.

 - **Grade 2** hyperthyroidism events (and **Grade 2-4** hypothyroidism):
 - In hyperthyroidism, non-selective beta-blockers (e.g. propranolol) are suggested as initial therapy.
 - In hypothyroidism, thyroid hormone replacement therapy, with levothyroxine or liothyroinine, is indicated per standard of care.
 - **Grade 3-4** hyperthyroidism
 - Treat with an initial dose of IV corticosteroid followed by oral corticosteroids. When symptoms improve to Grade 1 or less, steroid taper should be started and continued over no less than 4 weeks. Replacement of appropriate hormones may be required as the steroid dose is tapered.
- **Hepatic:**
 - For **Grade 2** events, monitor liver function tests more frequently until returned to baseline values (consider weekly).
 - Treat with IV or oral corticosteroids
 - For **Grade 3-4** events, treat with intravenous corticosteroids for 24 to 48 hours.
 - When symptoms improve to Grade 1 or less, a steroid taper should be started and continued over no less than 4 weeks.
- **Renal Failure or Nephritis:**
 - For **Grade 2** events, treat with corticosteroids.
 - For **Grade 3-4** events, treat with systemic corticosteroids.
 - When symptoms improve to Grade 1 or less, steroid taper should be started and continued over no less than 4 weeks.

- **Management of Infusion Reactions:** Signs and symptoms usually develop during or shortly after drug infusion and generally resolve completely within 24 hours of completion of infusion.

Table 5 below shows treatment guidelines for subjects who experience an infusion reaction associated with administration of pembrolizumab.

Table 5 Infusion Reaction Treatment Guidelines

NCI CTCAE v5.0 Grade	Treatment	Premedication at subsequent dosing
Grade 1 Mild reaction; infusion interruption not indicated; intervention not indicated	Increase monitoring of vital signs as medically indicated until the subject is deemed medically stable in the opinion of the investigator.	None
Grade 2 Requires infusion interruption but responds promptly to symptomatic treatment (e.g., antihistamines, NSAIDS, narcotics, IV fluids); prophylactic medications indicated for <=24 hrs	
Stop Infusion and monitor symptoms. Additional appropriate medical therapy may include but is not limited to:
 
 IV fluids Antihistamines NSAIDS Acetaminophen Narcotics 
Increase monitoring of vital signs as medically indicated until the subject is deemed medically stable in the opinion of the investigator. If symptoms resolve within one hour of stopping drug infusion, the infusion may be restarted at 50% of the original infusion rate (e.g., from 100 mL/hr to 50 mL/hr). Otherwise dosing will be held until symptoms resolve and the subject should be premedicated for the next scheduled dose.
 
Subjects who develop Grade 2 toxicity despite adequate premedication should be permanently discontinued from further trial treatment administration.
	
Subject may be premedicated 1.5h (\pm 30 minutes) prior to infusion of pembrolizumab with:
 
Diphenhydramine 50 mg po (or equivalent dose of antihistamine).
 
Acetaminophen 500-1000 mg po (or equivalent dose of antipyretic).

Grades 3 or 4 Grade 3: Prolonged (i.e., not rapidly responsive to symptomatic medication and/or brief interruption of infusion); recurrence of symptoms following initial improvement; hospitalization indicated for other clinical sequelae (e.g., renal impairment, pulmonary infiltrates) Grade 4: Life-threatening; pressor or ventilatory support indicated	
Stop Infusion. Additional appropriate medical therapy may include but is not limited to:
 
 IV fluids Antihistamines NSAIDS Acetaminophen Narcotics Oxygen Pressors Corticosteroids Epinephrine 
Increase monitoring of vital signs as medically indicated until the subject is deemed medically stable in the opinion of the investigator. Hospitalization may be indicated.
 
Subject is permanently discontinued from further trial treatment administration.
	No subsequent dosing
Appropriate resuscitation equipment should be available in the room and a physician readily available during the period of drug administration.		

